1 PROTOCOL SYNOPSIS

Primary Objective:	To evaluate the perioperative and post-operative radiographic and patient outcome variables with the K2M VESUVIUS® Demineralized Fibers when used with the K2M EVEREST® Spinal System as compared to literature reported outcomes using autograft with posterior stabilization in the treatment of spinal stenosis, spondylolisthesis (grade 1 or 2), and/or degenerative disc disease.
Study Design:	Prospective, non-randomized (single arm) multi-center study
Follow-Up Evaluations:	Clinical evaluations will be conducted at initial post-op, 3 months, 6 months, 12 months, and 24 months post-procedure. Adverse events will be monitored continuously.
Outcome Assessments:	
Outcome measurements include the following:
 
• Qualitative Radiographic and CT Assessments
○ Fusion Assessment○ Device Status• Oswestry Disability Index (ODI)• Back, Hip/Buttock, and Leg Pain 10cm Visual Analog Scale (VAS)• SF-12v2 Health Survey• Operative Assessments
○ Estimated Blood Loss○ Length of Operation○ Time of Anesthesia• Length of Hospital Stay• Functional and Economic Status and Return to Work/School• Use of Narcotics Post-Surgery• Patient Satisfaction
Safety Assessment:	
Safety will be assessed by:
 
• The evaluation of all adverse events including but not limited to device related, procedure related, and additional serious adverse events
Study Subjects:	Patients eligible for study enrollment will require pedicle screw fixation for posterior stabilization as an adjunct to fusion at one or two spinal levels (contiguous) for spinal stenosis, spondylolisthesis (grade 1 or 2), and/or degenerative disc disease (DDD). Qualified patients will be confirmed by history and radiographic assessment. Subjects under evaluation will be ≥ 18 years old at time of enrollment.
Device Evaluation Group:	VESUVIUS Demineralized Fibers (distributed by K2M, Inc. for LifeNet Health) used with the EVEREST Spinal System (K2M, Inc.) cleared for marketing and distribution under 510(k) K133944.
Comparative Group:	Historical, literature control of traditional spinal fusion intervention with posterior stabilization instrumentation and autograft.

Sample Size:

Two-hundred four (204) total subjects at up to 15 clinical sites, geographically distributed throughout the US. Sites are considered a Principal Investigator and their Sub-Investigators who are covered by a single Institutional Review Board's (IRB's) oversight and approval.

Subject enrollment will be capped so that no single site contributes more than approximately 15% of the cases.

Investigator Selection:

- Appropriate patient population for trial indication
- The Investigator must have completed a minimum of three surgeries using the EVEREST Spinal System. If a surgeon does not have experience with this, their first three (3) patients will be considered roll-in patients and the results from these patients will be analyzed against the entire cohort to determine if a learning curve exists. If a surgeon has previously completed three (3) surgeries using the EVEREST Spinal System, there will be no stratification of their data.
- Experience in clinical trial execution
- Dedicated research infrastructure
- Local institutional review board (IRB) for research oversight or ability to use central IRB
- Standard of Care (SOC) compatible with protocol requirements
 - Radiographic imaging per protocol
 - Use/Collection of patient reported outcome measures – ODI; Back, Hip/Buttock, and Leg VAS; SF-12v2
 - Follow-up evaluations at initial post-op, 3 months, 6 months, 12 months, and 24 months
- Insofar as possible, sites for the study will be distributed regionally and by type of institution and level of investigator experience, patient volume and research experience so that any unanticipated and potentially prognostic factors may then be balanced both geographically and demographically in the study

2 INTRODUCTION

2.1 Study Purpose

The purpose of this study is to evaluate fusion status and patient outcomes observed from use of the VESUVIUS Demineralized Fibers with the EVEREST Spinal System as compared to the literature reported outcomes of spinal fusion using autograft with posterior stabilization.

2.2 Background and Significance

Degenerative disc disease is a spinal condition caused by the breakdown of intervertebral discs. As a result of aging, the spine begins to show signs of wear and tear as the discs dry out and shrink. These age-related changes can lead to arthritis, disc herniation, or spinal stenosis, which can put pressure on the spinal cord and nerves and may cause back pain. Spinal fusion is often utilized as the final treatment after conservative method attempts have failed.

Although iliac crest graft is the gold standard for assisting instrumented fusion, alternatives to obviate the morbidity of graft harvest have become available. Specifically, the VESUVIUS Demineralized Fibers will be used in conjunction with the EVEREST Spinal System and results will be compared to those reported in literature after the utilization of autograft and posterior stabilization.

2.3 Device Description

VESUVIUS Fibers are sterile freeze-dried allografts that are processed from donated human tissue, resulting from the gift of an individual or his/her family. The EVEREST polyaxial screw provides an increased range of motion and features a CoCr head to minimize head splay, optimized dual lead thread designed to increase fixation in bone, an Easy-to-Start set screw facilitating set screw introduction, and the ability to accept both 5.5 mm and 6.0 mm diameter rods. Both K2M products are indicated for the uses described herein.

The EVEREST Spinal System was cleared for marketing under 510(k) K133944. The VESUVIUS Demineralized Fibers are a Human Cell and Tissue Based Product (HCT/P) that is distributed by K2M, Inc. for LifeNet Health.

2.4 Surgical Procedure

Implantation of the EVEREST Spinal System (K2M, Inc., Leesburg, VA) should be performed along with a posterolateral/transverse process fusion using VESUVIUS Demineralized Fibers (K2M, Inc., Leesburg, VA) as a graft extender. Implantation is performed according to the standard of care of the Investigator, and in accordance with K2M's Instructions for Use and Surgical Technique Manual for the EVEREST Spinal System and for the VESUVIUS Demineralized Fibers. The use of an interbody spacer is optional. If an interbody spacer is used, a biocompatible PEEK cage must be implanted using the transforaminal lumbar interbody fusion (TLIF) technique. Refer to Section 8.3, for further details of the surgical technique.

2.5 Indications for Use

VESUVIUS Demineralized Fibers are allograft material indicated for implantation in bony voids for tissue repair and are not intrinsic to the stability of the construct. Allograft is commonly used as a bone graft extender to augment insufficient volumes of local autograft. The EVEREST Spinal System may be used in conjunction with the RANGE® (MESA® and DENALI®) Spinal Systems, all of which are cleared for the following indications: Non-cervical fixation as an adjunct to fusion for the following indications: degenerative disc disease (defined as back pain of discogenic origin with degeneration of the disc confirmed by history and radiographic studies); spondylolisthesis; trauma (i.e., fracture or dislocation); spinal stenosis; curvatures (i.e., scoliosis, kyphosis and/or lordosis); tumor; pseudoarthrosis; and/or failed previous fusion.

Except for hooks, when used as an anterolateral thoracic/lumbar system the Everest Spinal System may also be used for the same indications as an adjunct to fusion. When used for posterior non-cervical pedicle screw fixation in pediatric patients the Everest Spinal System implants are indicated as an adjunct to fusion to treat adolescent idiopathic scoliosis. These devices are to be used with autograft and/or allograft. Pediatric pedicle screw fixation is limited to a posterior approach.

2.6 Benefits and Risks

2.6.1 Potential Benefits

There is no guarantee that the subject will experience any immediate or direct benefits with the use of the EVEREST Spinal System and/or the VESUVIUS Demineralized Fibers or for taking part in this study.

2.6.2 Potential Risks

Potential risks include those associated with any spinal surgery resulting in neurological, cardiovascular, respiratory, gastrointestinal compromise, or death. A full listing of potential risks of the device and the surgical procedure can be found in **Section 9.5 Potential Risks and Anticipated Adverse Events**.

2.7 Mitigation of Risks

Operative and acute periprocedural risks for the patients enrolled in this study are mitigated by restricting the use of the device to skilled neurological and orthopedic spine surgeons trained and experienced in the proper surgical technique to implant the respective device. Long-term risks such as device failure or pseudoarthrosis are mitigated by proper patient selection and implanting the device in accordance with the Surgical Technique Manual for the EVEREST Spinal System and use of the surgical instruments provided by K2M and by following accepted standard of care in this population for spinal fusion surgery.

3 INVESTIGATOR/SITE SELECTION

The Investigators selected to participate in this clinical study will be responsible for conducting the study according to the requirements of the protocol. Each site will have a designated Principal Investigator and may have Sub-Investigators. Investigators/sites will be selected for participation in the study according to the following criteria:

The Investigator/Site must have:

- Expertise in clinical areas relevant to the study, including a background in spine surgery, sufficient experience in clinical research and an adequate patient population with adult spine disorders
- Completed a minimum of three (3) surgeries using the EVEREST Spinal System. If a surgeon does not have experience with these, their first three (3) patients will be considered roll-in patients and the results from these patients will be analyzed against the entire cohort to determine if a learning curve exists. If a surgeon has previously completed three (3) surgeries using the EVEREST Spinal System, there will be no stratification of their data.
- Experience in participating in clinical studies and have adequate personnel and a dedicated research infrastructure including a Study Coordinator to adequately perform the tasks required by the clinical protocol
- Local institutional review board (IRB) for research oversight or ability to use central IRB
- A practice in a medical facility equipped appropriately to fulfill the surgical and patient contact requirements of the study
- A standard of care (SOC) compatible with or capable of complying with the protocol requirements including but not limited to:
 - Radiographic imaging per protocol
 - Use/Collection of patient reported outcome measures – ODI; Back, Hip/Buttock, and Leg VAS; SF-12v2
 - Follow-up evaluations at initial post-op, 3 months, 6 months, 12 months, and 24 months
- (Be willing to) sign a Clinical Research Agreement and abide by the agreement for the duration of the study.
- (Be willing to) provide financial disclosure; including updating the disclosure during the study if the financial status changes

The Investigators and practices in this trial are representative of the general user population of this type of device. Insofar as possible, sites for the study will be distributed regionally and by type of institution and level of investigator experience, patient volume and research experience so that any unanticipated and potentially prognostic factors may then be balanced both geographically and demographically in the study.

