3.1 Investigator Training

Training sessions in proper surgical technique and trial performance for the Principal Investigator, all Sub-Investigators and research coordinators will be provided by the sponsor prior to initiation of the study at each site.

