The TLIF approach with the EVEREST Spinal System also allows for auxiliary procedures for decompression of the spinal cord, correction of spondylolisthesis, correction of disc space collapse or mild kyphosis, as may be medically indicated.

Once the interbody implant is in place and bone graft added to the disc space, distraction is released and compression is applied to the pedicle screw to load the anterior implant and restore lordosis to the spine.

Posterolateral/Transverse Process Fusion and use of VESUVIUS Demineralized Fibers. For each level of the posterolateral fusion, local bone (amount used is to be estimated and recorded) is supplemented with VESUVIUS Demineralized Fibers and bone marrow aspirate (BMA)². The Fibers and BMA are to be combined in a 3:2 volumetric ratio (i.e., a minimum of 15cc Fibers and 10ml BMA are required for a one-level case). If BMA volumes are insufficient to achieve a 3:2 ratio, BMA may be supplemented with venous-line blood. The bone graft, extended with a minimum of 15cc VESUVIUS Fibers and 10ml BMA per level, is then evenly distributed to the right and left lateral gutters. Local bone may be obtained from the levels to be fused, as well as from no more than one additional level of decompression above the target level(s).

The interspinous ligament, if preserved, will serve to prevent graft migration into the exposed portion of the spinal canal and foramen. Care must be taken when placing graft on the ipsilateral intertransverse region to avoid allowing graft to enter the spinal canal or compress the exiting nerve root. Before closure, inspect the neurologic elements to ensure that no graft material has fallen into the spinal canal.

² Obtained from the anterior iliac crest and/or vertebral body (refer to detailed instructions provided in Appendix 1 of this protocol)

Surgical Close and Recovery. Standard procedures and precautions are to be followed for closure of the surgical incision and postoperative recovery. The patient is typically mobilized out of bed the day after surgery; bracing is not required but can be used according to surgeon preference. The subject may be instructed to return to normal activity at the discretion of the Investigator.

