8.3.1 Surgery/Hospital Discharge Evaluation

Surgery Data – Data points required on the Operative case report form must be documented at the time of surgery, including intra-operative adverse events.

- Date of Hospital Admission
- Date of Surgery
- Date of Hospital Discharge
- Implanting Surgeon
- Implanted System Details (screw and rod size, connector use, etc.)
- Surgery Detail/Concomitant Procedures
- Surgery Time (initial incision to closure)
- Anesthesia Time
- Perioperative Antibiotic Use
- Estimated Blood Loss
- Quantity of VESUVIUS Demineralized Fibers, Bone Marrow Aspirate and Local Bone Used
- Adverse Event Assessment

If the patient experienced an adverse event(s) during the hospitalization it should be documented and recorded on an Adverse Event case report form.

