12.2 Study Hypotheses

The primary study endpoint is the rate of fusion at 24 months. The primary hypothesis of this trial is that the fusion rate with the VESUVIUS Demineralized Fibers and the EVEREST Spinal System combination is non-inferior to the fusion rate achieved and reported with the traditional fusion utilizing autograft and posterior stabilization.

A PubMed literature review was conducted to assemble relevant publications utilizing results from posterior fusion surgeries incorporating osteobiologics. Searches included all peer-reviewed journals published between January 2000 and April 2013. Sample sizes, patient populations, evaluated variables, results, and recorded complications were assessed for each selected article. Only articles describing the use of autograft in comparable patient populations were incorporated into the results. The following table gives the fusion rates found during the literature review:

Papers*	Number of Cases	Number of Fusions	Fusion Rate
Paper 1 ¹	81	44	54.3%
Paper 2A ²	39	34	87.2%
Paper 2B	35	29	82.9%
Paper 3 ³	36	15	41.7%
Paper 4 ⁴	45	33	73.3%
Paper 5A ⁵	21	19	90.5%
Paper 5B	22	20	90.9%
Paper 6A ⁶	10	10	100.0%
Paper 6B	10	10	100.0%
Paper 7A ⁷	47	44	93.6%
Paper 7B	48	42	87.5%
Paper 8A ⁸	42	31	73.8%
Paper 8B	42	24	57.1%
Pooled	478	355	74.3%

* Refer to Appendix 2 for references

A total of 355 successes in 478 subjects gives an overall fusion rate of 74.3%. The hypotheses to be tested for this primary endpoint are as follows:

$$H_0: P_{K2M} \leq P_0 - \delta$$

$$H_A: P_{K2M} > P_0 - \delta$$

where P_{K2M} is the success rate of the VESUVIUS Demineralized Fibers and the EVEREST Spinal System combination, P_0 is the literature success rate of 74.3% and δ is the non-inferiority margin of 10% against the historical success rate.

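### The roll-in rule counts only prior EVEREST cases, so a surgeon with three of those and no VESUVIUS experience is left out of the planned learning-curve check

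*Combined protocol and SAP*

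**What the plan says.** Two places set the experience rule. The synopsis, under Investigator Selection, states: "The Investigator must have completed a minimum of three surgeries using the EVEREST Spinal System". Section 3 repeats it: "Completed a minimum of three (3) surgeries using the EVEREST Spinal System". For a surgeon without that experience, "their first three (3) patients will be considered roll-in patients and the results from these patients will be analyzed against the entire cohort"; the stated purpose is to find out whether there is a learning curve. For the others, section 3 says: "If a surgeon has previously completed three (3) surgeries using the EVEREST Spinal System, there will be no stratification of their data".

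EVEREST is the pedicle-screw system (section 2.3). VESUVIUS is the allograft fiber product, and it has preparation steps of its own. Section 8.3 says "The Fibers and BMA are to be combined in a 3:2 volumetric ratio", and Appendix 1 describes marrow aspiration and cautions that a wetter mix handles poorly.

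The primary hypothesis in section 12.2 is about both products: "The primary hypothesis of this trial is that the fusion rate with the VESUVIUS Demineralized Fibers and the EVEREST Spinal System combination is non-inferior" to autograft with posterior stabilization.

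**The concern.** Posterior stabilization is present on both sides of the comparison, so the graft is what chiefly separates the study treatment from the historical control. The learning-curve check is keyed to the other component. A surgeon who has placed EVEREST screws three times and has never used VESUVIUS is not a roll-in, and the plan says that this surgeon's data will not be stratified.

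Where roll-ins do exist, their surgeons are new to EVEREST and may be new to VESUVIUS as well. A difference seen in their first three patients could then come from the screws, the graft or both.

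What is at stake is the plan's own aim of finding out whether a learning curve exists. A report of no learning curve under this rule would say nothing reliable about the graft.

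**Working it through.** **1. Is early graft use identified anywhere else?** The other relevant places are:

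| Place | What it provides | Separates early from later graft cases? |
|---|---|---|
| 2.7 | Surgeons trained and experienced with the device concerned; no graft case count | No |
| 3.1 | "Training sessions in proper surgical technique and trial performance for the Principal Investigator, all Sub-Investigators and research coordinators" | No, it is given to everyone |
| 8.3, Appendix 1 | Standard graft preparation | No |
| 8.3.1 | "Implanting Surgeon", date of surgery, and quantities of fibers, marrow aspirate and local bone | Not as planned, but surgeon and date allow it |
| 12.7 | Descriptive look at covariates of interest; the example is the anterior spacer | Not named |
| 12.8 | Poolability by site | No, not by surgeon or case order |

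Section 12 contains no learning-curve analysis. Prior VESUVIUS use is not listed as a data item.

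**2. How many cases could be involved? (illustration)** The plan gives 204 subjects and up to 15 sites. The number of surgeons and their VESUVIUS experience are not given. Assume one or two surgeons per site at 15 sites, all new to VESUVIUS:

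- 15 × 3 = 45 first-three cases; 45/204 = 22%.
- 30 × 3 = 90 first-three cases; 90/204 = 44%.

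If all of them have three EVEREST cases, none of the 45 or 90 is flagged.

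**3. Does the gap touch the primary test?** First, the plan's own figure (section 12.3: more than 80% power at n = 173). For a one-sided 0.05 exact test of P ≤ 0.643, the smallest r with P(X ≥ r | 0.643) ≤ 0.05 is 123. The exact level is 0.0354, and P(X ≥ 123 | 0.743) = 85.3%. The plan's statement is reproduced.

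Now suppose that the 45 early cases fuse less often by d and all others fuse at 74.3%. The overall rate is 0.743 − d × 45/204:

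| d | Overall rate | Power at n = 173 |
|---|---|---|
| 0 | 74.3% | 85.3% |
| 5 points | 73.2% | 76% |
| 10 points | 72.1% | 65% |
| 20 points | 69.9% | 40% |

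Poorer early cases make the 64.3% bound harder to clear. They do not make a false claim of non-inferiority easier.

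**4. What could an early-versus-later comparison show?** Take 45 early against 159 later cases, with rates of 64.3% and 74.3% and two-sided 0.05 (normal approximation).

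- Pooled rate: (45 × 0.643 + 159 × 0.743)/204 = 0.721.
- SE under no difference: √[0.721 × 0.279 × (1/45 + 1/159)] = 0.0757.
- SE under the alternative: √[0.643 × 0.357/45 + 0.743 × 0.257/159] = 0.0794.
- Power: Φ[(0.10 − 1.96 × 0.0757)/0.0794] = Φ(−0.61) = 27%.

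With 90 against 114, the same formula gives 34%. For 80% power with 45 against 159, the early rate would have to be about 52%. These figures treat all 204 subjects as evaluable; losses would lower the power further.

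**The case against.** The strongest case for leaving the plan alone has four parts.

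- **The tested product is the combination.** EVEREST experience is therefore relevant, and section 2.5 describes the fibers as not contributing to construct stability. A screw-system threshold is a defensible qualification rule. This stands: the rule covers one of two components, and the point concerns only surgeons with at least three EVEREST cases and no VESUVIUS experience.
- **No harm is documented.** Nothing says that any surgeon is new to VESUVIUS, which is already distributed, or that early graft cases fuse less often. The mixing note in Appendix 1 is an instruction and gives no evidence of a learning effect. This also stands, so the size of any effect is unknown.
- **Other controls exist.** Preparation is standardized, graft quantities are recorded for every case, and section 12.7 would permit a look at case order. These narrow the gap, but none commits the plan to examining case order.
- **The investigators are meant to represent general users** (section 3), so including first-time graft users fits the aim. That is a reason to keep them in the primary analysis. It does not answer the learning-curve question.

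Section 3 uses a plural pronoun for the missing experience where the synopsis uses a singular one, so it might be read as covering both products. The sentences on either side name EVEREST only.

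Two stronger readings are tempting. A reader might infer that unflagged early cases bias the primary result towards success; step 3 of the working shows the opposite direction. A reader might also calculate how far the roll-in contrast is diluted. If 5 of 15 surgeons were new to EVEREST and all were new to VESUVIUS, 30 of the 189 non-roll-in subjects would be early graft cases, and 1 − 30/189 = 84% of a graft effect would remain. With 10 of 30 surgeons it would be 1 − 60/174 = 66%. The documents do not support using these factors. They rest on stacked assumptions about surgeons, and they treat the roll-in difference as a pure graft effect when those surgeons are also new to the screws.

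**Conclusion.** The concern holds in a limited form. As written, the check cannot speak for the graft: surgeons with three EVEREST cases and no VESUVIUS experience are not examined, and in roll-ins new to both products the two effects cannot be separated. This rests on the text and needs no calculation.

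The consequence is confined to the stated learning-curve aim. The primary test, its bound and the sample size are unaffected. The 22% to 44% of subjects is an illustration that assumes 15 sites, one or two surgeons each and no prior VESUVIUS use. The documents do not establish that a graft learning curve exists. This is a minor point, worth making because the remedy is cheap.

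**What to change.** In the synopsis (Investigator Selection) and section 3, replace the sentence that rules out stratification with a pre-specified descriptive comparison, for all surgeons, of each surgeon's first three study cases with that surgeon's later study cases, on 24-month fusion and safety. Case order follows from implanting surgeon and date of surgery, which are already on the operative form.

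Record each surgeon's prior VESUVIUS and EVEREST case counts at site qualification and show the table by both. Without the VESUVIUS count, surgeons who already use the fibers would be split by case order as though they were new, and the contrast would be diluted by an unknown amount. Keep the EVEREST roll-in comparison as a second factor.

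State in advance that the comparison is descriptive and has low power (about 27% for 64.3% against 74.3% with 45 and 159 subjects), so that finding no difference is not read as evidence of no learning curve.

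Surgeon qualification, the primary analysis set and the primary test stay as they are. The cost is wording in two places, one extra table and one extra item at site qualification.
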